#### IRB Determination of NSR in Previous Studies

Although a 510(k) application was submitted to the FDA in August 2015, due to the lengthy process entailed in the de novo FDA process, it is unlikely FDA approval will be issued in advance of the study start date. The investigators note, however, that all five of the IRBs at the aforementioned study sites involved in the FDA trials determined the exoskeleton to be non-significant risk (NSR).

Additionally, the Vanderbilt IRB has reviewed a number of prior related studies (since 2009) involving the Indego exoskeleton, and predecessors to it. In every case, the intervention has been determined to be non-significant risk (NSR), including active studies IRB no. 150089 and 140856, and former studies 091519 and 120343. The determination of NSR has additionally been substantiated by the fact that no injuries or serious adverse events have occurred during any of those studies, which collectively encompass hundreds of hours of exoskeleton use over a period of several years, and with approximately ten to fifteen different SCI subjects of varying injury levels.

#### **4.0 Inclusion/Exclusion Criteria**

##### Inclusion Criteria:

- Age 18 years or older.
- Size and limb proportions capable of fitting in the exoskeletal device :
  - Height between 1.55 m (5 ft, 1 in) and 1.92 m (6 ft, 3 in).
  - Femur length between 37.5 cm (15 in) and 43.125 cm (17.25 in).

- Body mass no greater than 114 kg (250 lb).
- Non-ambulatory or poorly-ambulatory. In this study, “non-ambulatory” is defined as a person who cannot walk, or is classified with a Functional Independence Measure (FIM) Gait score 1; “poorly ambulatory” is defined as a person with FIM Gait 2- 6, who may be able to walk short distances with or without braces or stability aid, or may be able to walk with assistance of one person, but whose primary means of mobility is a manual or power-operated wheelchair.
- Sufficient upper extremity strength and coordination to balance using appropriate stability aids, such as a rolling walker or forearm crutches, during exoskeleton walking.
- Present with SCI and NLI C5 or lower, with AIS A, B, C or D (as per the International Standard for Neurological Classification of SCI, ISNCSCI), who are non-ambulatory or poorly ambulatory.
- Chronic SCI: at least 6 months post-injury, and preferably post-injury more than 1 year.
- Sufficient bone health for walking with full weight-bearing without undue risk of fracture, as determined by each subject’s personal medical doctor, and approved by each site’s medical supervisor.
- Passive range of motion (PROM) at shoulders, trunk, upper extremities and lower extremities within functional limits for safe gait and use of appropriate assistive device/stability aid.
- Skin intact where interfacing with robotic device.
- MAS for spasticity score 3 or less in lower extremities.
- Blood pressure and heart rate within established guidelines for locomotor training:
  - At rest: systolic 150 mmHg or less, diastolic 90 mmHg or less, heart rate 105 bpm or less.
  - During exercise: systolic 180 mmHg or less, diastolic 105 mmHg or less, heart rate 145 bpm or less.
- Ability to tolerate an upright standing position for 20 min, passive or active, without being lightheaded or having a headache.
- Sufficient responsiveness to FES in the quadriceps, hamstrings, tibialis anterior, and gastrocnemius, as defined by MMT in response to stimulation of 3 or greater on a 5-point MMT scale. Note that this is specifically for Study 2, but is included in Study 1 in order to economize study resources regarding enrollment, training, and assessment, as previously discussed.
- Access to a wireless internet connection. Note that is required only for Study 3, but is included in Study 1 in order to economize study resources regarding enrollment, training and assessment, as previously discussed.

**Exclusion Criteria:**

- Heterotopic ossification that, in the opinion of the site medical supervisor, would place the subject at undue risk for fracture.
- Inability to follow instructions.
- Colostomy bag.
- Women who are pregnant or attempting to become pregnant during the course of the study. Note that a pregnancy test will be required and must be negative for all women prior to enrolling in the study, and will be additionally required and must be negative every four weeks during the course of the study protocol.
- Any disease, concomitant injury, or condition that interferes with the performance or interpretation of the protocol- specified assessments.
- Insufficient availability to complete study.
- Any other issue which, in the opinion of the investigators or medical supervisor, make the subject unsuitable for study participation.

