## 6.0 Study Procedures

### Design:

This study will include 24 non-ambulatory or poorly-ambulatory individuals with chronic SCI, i.e., at least 6 months post-injury, 12 with complete and 12 with incomplete SCI, to assess the mobility and therapeutic benefits resulting from exoskeleton use in a clinical setting. Changes in physiological and neurological status will be assessed via measurements taken pre-, mid-, and post- the 8-week intervention, as well as 8 weeks post-treatment. At all study sites, subject enrollment will begin following IRB approval, with 8 subjects enrolled at each of the 3 sites. Following IRB approval and enrollment, the study is expected to occur over an 18-month period. The treatment for each subject will consist of 31 sessions spanning 18 weeks in total, comprising a combination of 4 assessment, 3 training, and 24 treatment sessions. The 24 treatment sessions each consists of approximately 1 hour of walking in the exoskeleton, although 1.5 hours are allotted to account for donning/doffing, measurement of vital signs, skin checks, etc., and will be delivered 3 times per week over an 8-week period.

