### Intervention

The intervention will be carried out identically at all sites and will be comprised of 31 sessions at the subjects' trial site, including 4 assessment sessions (pre, mid, immediately post treatment, and 8 weeks post-treatment), 3 exoskeleton fitting/training sessions, and 24 intervention sessions. The interventions at each site will be administered by a PT experienced in locomotor training for individuals with SCI. Parker Hannifin will provide exoskeleton-specific training at each site, in order to ensure safe, effective implementation and use of the exoskeletons. A summary of each session's activity and measurements follows:

- Session 1: Informed consent and pre-treatment health and neurological assessment, including PT evaluation and Dexa Scan (x-ray picture of the bone) of the distal femur and proximal tibia locations, and drawing about 2 teaspoons (9.5 mL) of blood to check A1C (measures the amount of hemoglobin in the blood that has glucose attached to it) and Lipid Panel to measure cholesterol levels (lasting 4 hrs).
- Sessions 2-4: Exoskeleton fitting, adjustment, and training sessions (3 sessions per week lasting 1.5 hours per session)
- Sessions 5-16: Exoskeleton treatment consisting of walking in the exoskeleton during a 1.5-hr session, with breaks as needed, and with sit-to-stand, turning, and stand-to-sit maneuvers as appropriate (3 sessions per week lasting 1.5 hours). Note that sessions 15 and 16 are additionally used for assessment of the mobility provided by the exoskeleton.
- Session 17: Mid-treatment health and neurological assessment (lasting 3-4 hours).
- Sessions 18-29: Exoskeleton treatment consisting of walking in the exoskeleton during a 1.5-hour session, with breaks as needed, and with sit-to-stand, turning, and stand-to-sit maneuvers as appropriate (3 sessions per week lasting 1.5 hours per session). Note that sessions 28 and 29 are also used for assessment of the mobility provided by the exoskeleton.

- Session 30: Post-treatment health and neurological assessment, within 3 days of session 29, including Dexa Scan (x-ray picture of the bone) of the distal femur and proximal tibia locations, and 2 teaspoons (9.5 mL) of blood to check A1C (measures the amount of hemoglobin in the blood that has glucose attached to it) and Lipid Panel to measure cholesterol levels (lasting 3-4 hours).

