- Session 31: Follow-up health and neurological assessment, including Dexa Scan (x-ray picture of the bone) of the distal femur and proximal tibia locations, and 2 teaspoons (9.5 mL) of blood to check your A1C (measures the amount of hemoglobin in the blood that has glucose attached to it) and Lipid Panel to measure cholesterol levels, 8 weeks following session 30 (lasting 3-4 hours).

Women of child bearing potential will have a urine pregnancy test at baseline, and in sessions 17, 30 and 31.

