#### Measures assessing level of mobility enabled by the exoskeleton to include the following, all measured while subject is using the exoskeleton:

- The 10MWT as a measure of gait speed.
- The TUG test measures ability to independently sit, stand, walk, turn, and return to sitting. The TUG test will be used as a measure of mobility independence.

- The 6MWT measures gait speed over a six-minute period. This test provides a controlled measure of endurance, and provides a secondary measure of gait speed.
- The BRPE measures perceived exertion during walking and will be assessed in this protocol during the 6MWT.

Additional measures taken during each session will include:

- Vital signs at start of each session (blood pressure and heart rate)
- Number of steps taken during each training session (measured by exoskeleton)
- Monitoring of skin integrity at exoskeleton contact points, following each session

Schedule of Assessments

The study will include 4 primary assessments characterizing health and neurological effects of exoskeleton use, in addition to 2 primary assessments characterizing level of mobility provided by the exoskeleton. The assessments characterizing potential health include DXA, MAS, SCI-SET tests, weight, and a self-report questionnaire. The assessments characterizing potential neurological or functional recovery include the MMT and FR tests, and for poorly-ambulatory subjects, also include the FIM-G, WISCI-II, 10MWT, and TUG tests, all performed without the exoskeleton. This battery of assessments is expected to require 3-4 hours, and will occur 4 times during the study as follows: pre-treatment (at study start, session 1), mid-treatment (after 4 weeks of treatment, session 17), post-treatment (after 8 weeks of treatment, session 30), and 8 weeks post-treatment (session 31). Note that DXA will not be measured at mid-treatment, in order to mitigate associated costs, since an 8-week interval is a short enough period of time relative to characteristic time scales associated with changes in BMD. Note that treatment will not occur on these assessment days, i.e., the exoskeleton will not be used on these days. Finally, the MAS will be administered on these 4 days, and also on 3 additional days, each immediately following exoskeleton use associated with a treatment session, at the start, mid-point, and end of treatment.

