In addition to assessment of health, neurological and functional status, additional assessments will be performed to characterize the level of mobility provided by the exoskeleton. These assessments include the FIM-G, WISCI-II, 10MWT, 6MWT, TUG, and BRPE tests, all performed while the subject is wearing the exoskeleton. The battery of mobility assessments will occur within the standard treatment sessions at treatment midpoint (i.e., after 4 weeks of treatment, during sessions 15 and 16) and at treatment end (i.e., after 8 weeks of treatment, during sessions 28 and 29). Note that the TUG test is performed on a separate day from the other assessments, to mitigate the number of tests to complete in a single session. Note also that the 10MWT will be administered once during each quarter of treatment, since the test is informative and easily administered, and thus will not substantially disrupt a session of typical exoskeleton treatment.

The scheduling of assessment for each subject is provided in the chart below.

	Outcome Measure	Baseline	Fitting and Training	Treatment (12 sessions)												Mid-treatment	Treatment (12 sessions)															
				Treatment (12 sessions)														Treatment (12 sessions)														
Health effects	DXA																															
	MAS																															
	SCI-SET																															
	Weight																															
	Bloodwork																															
	Self-report																															
Neurological recovery	Neuro exam																															
	FR																															
Neurological recovery for poorly-ambulatory	FIM-G w/o Exo																															
	WISCI-II w/o Exo																															
	10MWT w/o Exo																															
	TUG w/o Exo																															
Mobility (in exoskeleton)	FIM-G																															
	WISCI-II																															
	10MWT																															
	6MWT																															
	TUG																															
Other	BRPE																															
	Steps																															
	Skin																															
	Vital signs																															
	Total session	1	2	3	4	5	6	7	8	9	10	11	12	13	14	15	16	17	18	19	20	21	22	23	24	25	26	27	28	29	30	31
	Total week	1	2	2	2	3	3	3	4	4	4	5	5	5	6	6	6	7	7	7	8	8	8	9	9	9	10	10	11	11	18	
	Treatment session																															
	Treatment week	1	1	1	2	2	2	3	3	3	4	4	4	4	5	5	5	6	6	6	7	7	7	8	8	8	8	8	8	8		

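### The listed pregnancy tests fall about 5–6, 4 and 8 weeks apart and so miss the protocol's own four-weekly rule in the first and third intervals

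*Protocol*

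**What the plan says.** The Exclusion Criteria in Protocol section 4.0 exclude women who are pregnant or trying to become pregnant. They add that "a pregnancy test will be required and must be negative for all women prior to enrolling in the study", and that a further test "must be negative every four weeks during the course of the study protocol".

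The visit-level instruction is at the end of section 6.0, Intervention: "Women of child bearing potential will have a urine pregnancy test at baseline, and in sessions 17, 30 and 31". No other pregnancy test is described in either document, and the readable row labels of the assessment chart include none.

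The timing of those visits comes from section 6.0. Under Design: "The treatment for each subject will consist of 31 sessions spanning 18 weeks in total". Schedule of Assessments places the later visits at "mid-treatment (after 4 weeks of treatment, session 17), post-treatment (after 8 weeks of treatment, session 30), and 8 weeks post-treatment (session 31"). The Intervention list puts a training block and the first half of treatment between baseline and session 17: "Sessions 2-4: Exoskeleton fitting, adjustment, and training sessions (3 sessions per week lasting 1.5 hours per session"), then "Sessions 5-16: Exoskeleton treatment consisting of walking in the exoskeleton during a 1.5-hr session", also three per week.

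**The concern.** Pregnancy is an exclusion, and the four-weekly test is the protocol's stated means of detecting it after enrolment. The rule runs over the study protocol, which lasts 18 weeks per subject and includes follow-up. The list appears to have been tied to the four main assessment visits. Session 17 is timed from the start of treatment, not from baseline, and the last two visits are eight weeks apart. If the intervals exceed four weeks, a site can carry out every listed test and still break the criterion. With three sites meant to run an identical protocol, one might add tests and another might not.

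The two places also name different groups: all women in section 4.0, women of child-bearing potential in section 6.0. That is a wording point, but it leaves unclear who is to be tested.

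**Working it through.** The plan's own figure is a maximum interval of four weeks, or 28 days. The check is whether the listed visits reproduce it.

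**Inputs (section 6.0).** Session 1 is baseline. Sessions 2–4 are training and sessions 5–16 treatment, both at three per week. Session 17 follows four weeks of treatment. Sessions 18–29 are treatment at three per week. Session 30 is within 3 days of session 29, and session 31 is 8 weeks after session 30.

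**Check without the chart.** Sessions 2–16 number 3 + 12 = 15, and 15 / 3 = 5 weeks. On a fixed weekday pattern, the shortest span from session 2 to session 16 is 4 × 7 + 2 = 30 days. Baseline lies before that span and session 17 after it, so the first interval exceeds 28 days.

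**Calendar (assumed).** Day 0 is Monday of week 1, and baseline falls on day 0–4. Sessions 2–4 are in week 2 and sessions 5–16 in weeks 3–6, on the same three weekdays each week; all ten three-weekday patterns are allowed. The week of session 17 is not certain. The extracted total-week row puts it in week 7 but has 30 entries for 31 sessions, and the treatment-week row can be read as week 6. Both placements are used.

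1. *Baseline to session 17.*
   - Week 7, first slot (day 42–44): 42 − 4 = 38 to 44 − 0 = 44 days.
   - Week 6, on a weekday after session 16 (day 38–39): 38 − 4 = 34 to 39 − 0 = 39 days.
   - Together 34–44 days, about 5–6 weeks.
2. *Session 17 to session 30* (Monday/Wednesday/Friday).
   - Session 17 on day 42, session 30 on day 71–73: 29–31 days.
   - Session 17 on the Saturday of week 6 (day 40), session 30 on day 68–70: 28–30 days.
   - About four weeks either way.
3. *Session 30 to session 31.* 8 × 7 = 56 days. The chart's weeks 11 and 18 would give 18 − 11 = 7 weeks, still over four.

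**Treatment sessions after the first four-week test is due.** These all precede session 17, so the week chosen for session 17 does not matter. On Monday/Wednesday/Friday, sessions 11–16 fall on days 28, 30, 32, 35, 37 and 39.

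- Strict cutoff, Monday baseline (due day 28): sessions 12–16, which is 5.
- Strict cutoff, Friday baseline (due day 32): sessions 14–16, which is 3.
- With 3 days' tolerance (due day 31 or 35): 4 or 2.
- A Tuesday/Wednesday/Thursday pattern with a Monday baseline and strict cutoff has sessions on days 29, 30, 31, 36, 37 and 38, which is 6.

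The range is 2–6. The tolerance matters because interval 2, at up to 31 days, is accepted here as about four weeks; the same leniency should be open to interval 1.

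**Placing an extra test.** Session 10 is the third session of week 4 (day 23–25), so it falls 23 − 4 = 19 to 25 − 0 = 25 days after baseline. Session 17 follows 17–19 days later if in week 7 (21 minus a within-week spread of 2–4 days), or 15–16 days later if on a weekday of week 6. Session 11 is the first session of week 5 (day 28–30), hence 24–30 days after baseline, which can already be late.

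**The case against.** The strongest defence is that the rule follows the treatment clock. The Study Outline describes the mid-treatment visit as the 4-week midpoint, and Schedule of Assessments dates sessions 17 and 30 from the start of treatment. On that reading the tests are at 0, 4 and 8 weeks, and the first excess is only the baseline and fitting lead-in. This probably explains how the list arose. It does not fit the wording of section 4.0, which speaks of the study protocol and not of treatment. It leaves out a training week in which the exoskeleton is already used, and it does nothing for the 8-week follow-up interval.

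A second defence is that nothing in section 6.0 says these four tests are the only ones, so a site could add more and satisfy both places. That stands. A reader might infer that the two instructions contradict each other; the documents do not support that. The list is incomplete, not irreconcilable with the rule.

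A reader might also infer that women are scanned without a current test. That is not supported either. DXA is scheduled at sessions 1, 30 and 31 and not at mid-treatment, and each of those visits has a listed test for women of child-bearing potential.

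Finally, the practical consequence is small: a test one to two weeks late during treatment, in an unstated number of women among 24 subjects, with women attempting pregnancy already excluded. That stands and sets the severity.

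**Conclusion.** The listed schedule misses the four-weekly rule in two of its three intervals: about 5–6 weeks from baseline to session 17, and 8 weeks from session 30 to session 31. The middle interval is about four weeks. That the first interval exceeds four weeks follows from the session counts alone. The 34–44 day range and the 2–6 sessions rest on assumed weekdays, on session 17 falling in week 6 or 7, and on a tolerance of 0–3 days, so they should be read as approximate.

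A reader might take the finding to mean that subjects face a demonstrated danger. The documents do not show that: they describe no pregnancy-specific risk of exoskeleton walking, and the longer interval contains no study sessions. The efficacy analysis does not depend on it. This is a minor safety-consistency correction.

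**What to change.** 1. In section 6.0, Intervention, add a urine pregnancy test at session 10.
2. In section 4.0, choose one option for follow-up. Either limit the four-weekly rule to the period through session 30 and keep the test before the session 31 DXA, or keep the rule to the end and add one test about four weeks after session 30.
3. State a window of a few days around each four-week due date, so that the session 17 to session 30 interval complies.
4. Use one population term in both sections.

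The follow-up choice and the population term are for the clinical lead. Rewording section 4.0 to name only the four listed visits would also remove the mismatch without an extra test, but it would give up the four-weekly check while the exoskeleton is in use.

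The cost is a short wording change and one extra urine test per affected woman at a visit she already attends. Only the optional mid-follow-up test has no existing visit. It would need a home test, or an added visit with the $25 payment and travel reimbursement described in section 5.0.

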## 5.0 Enrollment

Eight subjects will be recruited from the clinical practices and surrounding communities for each of the three data collection sites. Subjects will be enrolled if they satisfy the inclusion/exclusion criteria outlined above, and agree to the 18 week commitment for the study. Investigator patient lists, therapist and physician referrals, and medical record search engines will all be used to recruit potential subjects. In addition, subjects will be identified during outpatient clinical visits by study investigators. Subjects will be identified through lists and medical records. Once enrolled, subjects will be reimbursed \$25 per visit for their involvement, in addition to receiving mileage and parking reimbursement for travel to and from their trial sites.

## 6.0 Study Procedures

### Design:

This study will include 24 non-ambulatory or poorly-ambulatory individuals with chronic SCI, i.e., at least 6 months post-injury, 12 with complete and 12 with incomplete SCI, to assess the mobility and therapeutic benefits resulting from exoskeleton use in a clinical setting. Changes in physiological and neurological status will be assessed via measurements taken pre-, mid-, and post- the 8-week intervention, as well as 8 weeks post-treatment. At all study sites, subject enrollment will begin following IRB approval, with 8 subjects enrolled at each of the 3 sites. Following IRB approval and enrollment, the study is expected to occur over an 18-month period. The treatment for each subject will consist of 31 sessions spanning 18 weeks in total, comprising a combination of 4 assessment, 3 training, and 24 treatment sessions. The 24 treatment sessions each consists of approximately 1 hour of walking in the exoskeleton, although 1.5 hours are allotted to account for donning/doffing, measurement of vital signs, skin checks, etc., and will be delivered 3 times per week over an 8-week period.

